### 3.2.3.6 Rationale for re-treatment beyond 12 months

Justification for re-treatment beyond 12 months of MEDI4736:

- Targeted therapies have significantly increased both the rate and durability of response in patients with biomarker-enriched subsets of cancers including advanced NSCLC (eg, gefitinib and erlotinib in EGFR mutation positive, and crizotinib in ALK translocation positive) as well as in metastatic or unresectable melanoma (vemurafenib and dabrafenib in BRAF V600E mutation, trametinib in both V600E and V600K) (Maemondo et al 2010, Mok et al 2009, Mitsudomi et al 2010, Rosell et al 2011, Shaw et al 2013). Nevertheless, responses are mostly partial, and relapses are inevitable once resistance mechanisms emerge. Furthermore, the potential for tumour “addiction” and rapid clinical deterioration at the time of withdrawal and/or progression has been described (Asami et al 2013, Yoshimura et al 2013, Kim et al 2011, Yang et al 2013, Rizos et al 2014).
- In contrast to targeted therapy, responses have been observed upon re-treatment with immune-mediated therapy. Responses with immune-mediated therapy are no different than responses to initial treatment in terms of time to response, duration of response, or maintenance of response beyond treatment discontinuation (Hodi et al 2010, Forde et al 2014).

Therefore, patients who achieve and maintain disease control (ie, CR, PR or SD) through to the end of the 12-month study drug treatment period may also re-start treatment with study drug upon evidence of disease progression during follow-up.

The patient must not have received an intervening systemic anti-cancer therapy after discontinuing study drug and should have a baseline tumour assessment within 28 days of re-starting treatment with study drug (see Table 11).

## **4. PATIENT SELECTION CRITERIA**

The patient population should be selected without bias.

Investigator(s) should keep a record, the patient screening log, of patients who entered pre-study screening.

Each patient should meet all of the inclusion criteria and none of the exclusion criteria for this study. Under no circumstances can there be exceptions to this rule.

### **4.1 Inclusion criteria**

For inclusion in the study patients should fulfil the following criteria:

1. Provision of signed, written and dated informed consent prior to any study specific procedures
2. Male or female aged 18 years or older
3. Patients must have histologically- or cytologically-documented NSCLC who present with locally advanced, unresectable (Stage III) disease (according to Version 7 of the International Association for the Study of Lung Cancer Staging Manual in Thoracic Oncology [[IASLC Staging Manual in Thoracic Oncology](#)]), AND
4. Patients must have received at least 2 cycles of platinum-based chemotherapy concurrent with radiation therapy, which must be completed within 1 to 42 days prior to first dose of investigational product in the study. For patients who are recovering from toxicities associated with prior treatment, first dose of investigational product may be delayed by up to 42 days from the end of the chemoradiation therapy.

Sites are strongly encouraged to complete screening within the first 14 days of the 42-day screening period.

- The platinum-based chemotherapy regimen must contain one of the following agents: etoposide, vinblastine, vinorelbine, a taxane (paclitaxel or docetaxel), or pemetrexed, according to the local standard of care regimens.
- The final chemotherapy cycle must end prior to, or concurrently with, the final dose of radiation. Consolidation chemotherapy after radiation is not permitted but administration of chemotherapy prior to concurrent chemoradiation is acceptable.
- Where possible, chemotherapy regimens should be given according to National Comprehensive Cancer Network (NCCN) Guidelines or European Society for Medical Oncology (ESMO) Guidelines.

- Patients must have received a total dose of radiation of 60 Gy  $\pm$ 10% (54 Gy to 66 Gy) to be randomised as part of the chemoradiation therapy. Sites are encouraged to adhere to mean organ radiation dosing as follows:
  - Mean lung dose must be <20 Gy and/or V20 must be <35%
  - Mean esophagus dose must be <34 Gy
  - Heart V45 <35% or V30 <30%.
- Sites should be aware of the recent RTOG 0617 Trial data demonstrating that doses higher than 60 Gy may be associated with greater toxicity and worse efficacy.
- 5. Patients must have not progressed following definitive, platinum-based, concurrent chemoradiation therapy.
- 6. Tumour sample requirements:
  - Provision of an archived tumour tissue block (or at least 10 newly cut unstained slides) where such samples exist in a quantity sufficient to allow for analysis (refer to Section 6.7.1 and the Laboratory Manual for details)
  - A recent ( $\leq$ 3 months) tumour biopsy (taken following completion of the most recent therapy) is an optional requirement, provided that a biopsy procedure is technically feasible and the procedure is not associated with unacceptable clinical risk
- 7. Life expectancy  $\geq$ 12 weeks at Day 1
- 8. World Health Organization (WHO) Performance Status of 0 or 1
- 9. Evidence of post-menopausal status, or negative urinary or serum pregnancy test for female pre-menopausal patients. Women will be considered post-menopausal if they are amenorrhic for 12 months without an alternative medical cause. The following age-specific requirements apply:
  - Women <50 years old would be considered post-menopausal if they have been amenorrhic for 12 months or more following cessation of exogenous hormonal treatments and with luteinizing hormone and follicle-stimulating hormone levels in the post-menopausal range for the institution
  - Women  $\geq$ 50 years of age would be considered post-menopausal if they have been amenorrhic for 12 months or more following cessation of all exogenous hormonal treatments, radiation-induced oophorectomy with last menses >1 year ago, chemotherapy-induced menopause with >1 year interval since last menses, or surgical sterilisation (bilateral oophorectomy or hysterectomy).

10. Adequate organ and marrow function as defined below:

- Absolute neutrophil count  $>1.5 \times 10^9/L$  (1500 per  $mm^3$ )
- Platelets  $>100 \times 10^9/L$  (100,000 per  $mm^3$ )
- Haemoglobin  $\geq 9.0$  g/dL (5.59 mmol/L)
- Serum creatinine CL  $>40$  mL/min by the Cockcroft-Gault formula (Cockcroft and Gault 1976) or by 24-hour urine collection for determination of creatinine clearance:

Males:

$$\text{Creatinine CL (mL/min)} = \frac{\text{Weight (kg)} \times (140 - \text{Age})}{72 \times \text{serum creatinine (mg/dL)}}$$

Females:

$$\text{Creatinine CL (mL/min)} = \frac{\text{Weight (kg)} \times (140 - \text{Age})}{72 \times \text{serum creatinine (mg/dL)}} \times 0.85$$

- Serum bilirubin  $\leq 1.5$  x upper limit of normal (ULN). This will not apply to patients with confirmed Gilbert's syndrome (persistent or recurrent hyperbilirubinaemia that is predominantly unconjugated in the absence of evidence of haemolysis or hepatic pathology) who will be allowed in consultation with their physician.
- AST and ALT  $\leq 2.5$  x ULN.

#### Genetics research study (optional)

For inclusion in the optional (DNA) genetics research study patients must fulfil the following criteria:

- Provide informed consent for the genetic sampling and analyses.

If a patient declines to participate in the genetics research, there will be no penalty or loss of benefit to the patient. A patient who declines genetics research participation will not be excluded from any other aspect of the main study.

## 4.2 Exclusion criteria

Patients should not enter the study if any of the following exclusion criteria are fulfilled:

1. Involvement in the planning and/or conduct of the study (applies to both AstraZeneca/MedImmune staff and/or staff at the study site).
2. Either:

- Previous drug assignment in the present study

or

- Prior randomisation or treatment in a previous durvalumab (MEDI4736) and/or tremelimumab clinical study regardless of treatment arm assignment
3. Participation in another clinical study with an investigational product during the last 4 weeks.
  4. Concurrent enrolment in another clinical study, unless it is an observational (non-interventional) clinical study or the follow-up period of an interventional study.
  5. Mixed small cell and non-small cell lung cancer histology.
  6. Patients who receive sequential chemoradiation therapy for locally advanced NSCLC.
  7. Patients with locally advanced NSCLC who have progressed whilst definitive platinum based, concurrent chemoradiation therapy.
  8. Receipt of any immunotherapy, or investigational drug within 4 weeks prior to the first dose of study drug; and in the case of monoclonal antibodies 6 weeks prior to the first dose of study drug.
  9. Current or prior use of immunosuppressive medication within 28 days before the first dose of study drug, with the exceptions of intranasal and inhaled corticosteroids or systemic corticosteroids at physiological doses, which are not to exceed 10 mg/day of prednisone, or an equivalent corticosteroid. Systemic steroid administration required as prophylaxis against or to manage toxicities arising from chemotherapy and/or radiotherapy delivered as part of the chemoradiation therapy for locally advanced NSCLC is allowed.
  10. Prior exposure to any anti-PD-1 or anti-PD-L1 antibody.
  11. Any unresolved toxicity CTCAE >Grade 2 from the prior chemoradiation therapy. Patients with irreversible toxicity that is not reasonably expected to be exacerbated by study drug may be included (eg, hearing loss) after consultation with the AstraZeneca/MedImmune medical monitor.
  12. Patients with  $\geq$ grade 2 pneumonitis from prior chemoradiation therapy.
  13. Any prior Grade  $\geq$ 3 immune-related adverse event (irAE) while receiving any previous immunotherapy agent, or any unresolved irAE >Grade 1.

14. Any concurrent chemotherapy, immunotherapy, biologic or hormonal therapy for cancer treatment.
15. Recent major surgery within 4 weeks prior to entry into the study (excluding the placement of vascular access) that would prevent administration of study drug.
16. Active or prior documented autoimmune disease within the past 2 years.  
NOTE: Patients with vitiligo, Grave's disease, or psoriasis not requiring systemic treatment (within the past 2 years) are not excluded.
17. Active or prior documented inflammatory bowel disease (eg, Crohn's disease, ulcerative colitis).
18. History of primary immunodeficiency.
19. History of allogeneic organ transplant.
20. History of hypersensitivity to MEDI4736 or any excipient.
21. Mean QT interval corrected for heart rate (QTc)  $\geq 470$  ms calculated from 3 electrocardiograms (ECGs) using Bazett's Correction.
22. Uncontrolled intercurrent illness including, but not limited to, ongoing or active infection, symptomatic congestive heart failure, uncontrolled hypertension, unstable angina pectoris, cardiac arrhythmia, active peptic ulcer disease or gastritis, active bleeding diatheses including any patient known to have evidence of acute or chronic hepatitis B, hepatitis C or human immunodeficiency virus (HIV), or psychiatric illness/social situations that would limit compliance with study requirements or compromise the ability of the patient to give written informed consent.
23. Active infection of tuberculosis, as determined by clinical signs and symptoms.
24. Receipt of live attenuated vaccination within 30 days prior to study entry or within 30 days of receiving study drug.
25. History of another primary malignancy except for:
  - Malignancy treated with curative intent and with no known active disease  $\geq 5$  years before the first dose of study drug and of low potential risk for recurrence
  - Adequately treated non-melanoma skin cancer or lentigo maligna without evidence of disease
  - Adequately treated carcinoma in situ without evidence of disease eg, cervical cancer in situ.

26. Female patients who are pregnant, breast-feeding or male or female patients of reproductive potential who are not employing an effective method of birth control.
27. Any condition that, in the opinion of the Investigator, would interfere with evaluation of the study drug or interpretation of patient safety or study results.

### **Genetics research study (optional)**

Exclusion criteria for participation in the optional (DNA) genetics research component of the study:

- Previous allogeneic bone marrow transplant
- Non-leukocyte depleted whole blood transfusion in 120 days of genetic sample collection.

Procedures for withdrawal of incorrectly enrolled patients are provided in Section 5.3.

### **4.3 Criteria for treatment through progression of disease and re-treatment**

Patients with rapid tumour progression or with symptomatic progression that requires urgent medical intervention (eg, central nervous system metastasis, respiratory failure due to tumour compression, spinal cord compression) will not be eligible for continuing study drug.

For all patients who completed the first 12-month period of treatment with study drug and had CR, PR or SD at completion, re-treatment during follow up would be offered on the basis of a patient having objective RECIST 1.1 disease progression with or without confirmation.

For all patients who are treated through progression, or patients who achieve disease control [ie, CR, PR, or SD] at 12 months and restart treatment upon evidence of PD during follow-up, the Investigator should ensure patients do not have any significant, unacceptable or irreversible toxicities that indicate continuing or restarting treatment would not further benefit the patient. In addition, the Investigator should ensure patients meet the following inclusion criteria (criteria number from Section 4.1):

- The patient must provide signed, written and dated re-treatment or treatment through progression informed consent (criterion 1). These consent documents will specify that treatment beyond initial evidence of PD or re-treatment upon progression during follow up is not the standard of care and that alternative treatment options, either locally licensed treatments or other clinical trials, are available for this patient population.
- Meet serum creatinine CL >40 mL/min by the Cockcroft-Gault formula (or by 24-hour urine collection as defined by the formula in protocol inclusion criterion 10) and the criterion for AST/ALT.

The patient should not enter re-treatment if any of the following exclusion criteria are fulfilled:

- Concurrent enrolment in another clinical study, unless it is an observational (non-interventional) clinical study or the follow-up period of an interventional study (criterion 4)
- Current or prior use of immunosuppressive medication within 28 days before the first dose of study drug, with the exceptions of intranasal and inhaled corticosteroids or systemic corticosteroids at physiological doses, which are not to exceed 10 mg/day of prednisone, or an equivalent corticosteroid (criterion 9)
- Any unresolved toxicity CTCAE >Grade 2 from previous anti-cancer therapy. Patients with irreversible toxicity that is not reasonably expected to be exacerbated by the investigational product may be included (eg, hearing loss) after consultation with the AstraZeneca/MedImmune study physician (criterion 11)
- Any prior Grade  $\geq 3$  irAE while previously receiving study treatment, or any unresolved irAE >Grade 1 (criterion 13)
- Be currently receiving, or have received in the interim period after stopping study drug, any chemotherapy, immunotherapy, biologic or hormonal therapy for cancer treatment. Note: Local treatment of isolated lesions, excluding target lesions, for palliative intent is acceptable (eg, by local surgery or radiotherapy) (drawn from criterion 14)
- Recent major surgery within 4 weeks prior to dosing (excluding the placement of vascular access) that would prevent administration of investigational product (criterion 15)
- Active or prior documented autoimmune disease within the past 2 years (patients with vitiligo, Grave's disease, or psoriasis not requiring systemic treatment within the past 2 years are not excluded) (criterion 16)
- Active or prior documented inflammatory bowel disease (eg, Crohn's disease, ulcerative colitis) (criterion 17)
- History of primary immunodeficiency (criterion 18)
- History of allogeneic organ transplant (criterion 19)
- History of hypersensitivity to MEDI4736 or any excipient (criterion 20)
- Mean QT interval corrected for heart rate (QTc)  $\geq 470$  ms calculated from 3 electrocardiograms (ECGs) using Bazett's Correction (criterion 21)

- Uncontrolled intercurrent illness including, but not limited to, ongoing or active infection, symptomatic congestive heart failure, uncontrolled hypertension, unstable angina pectoris, cardiac arrhythmia, active peptic ulcer disease or gastritis, active bleeding diatheses including any patient known to have evidence of acute or chronic hepatitis B, hepatitis C or human immunodeficiency virus (HIV), or psychiatric illness/social situations that would limit compliance with study requirements or compromise the ability of the patient to give written informed consent (criterion 22)
- Active infection of tuberculosis, as determined by clinical signs and symptoms (criterion 23)
- Receipt of live attenuated vaccination within 30 days prior to dosing or within 30 days of receiving study drug (criterion 24)
- Female patients who are pregnant, breast-feeding or male or female patients of reproductive potential who are not employing an effective method of birth control (criterion 26)
- Any condition that, in the opinion of the Investigator, would interfere with evaluation of the investigational product or interpretation of patient safety or study results (criterion 27).

At the time of the final DCO for the primary analyses of PFS and OS, study patients randomised to the durvalumab arm who have not progressed and who meet the above eligibility criteria will remain in the study. At the time the patient progresses, and re-treatment with durvalumab is felt to be their best treatment option, then at the time of re-treatment they must meet the above eligibility criteria. Patients' eligibility should be recorded in their medical records. Re-treatment will not be available within this protocol following the final DCO for the long-term follow-up phase of the study (CSP amendment 7).

Study drug should be discontinued if there is confirmed PD while on treatment following a previous response (PR or CR) to study drug while on treatment (ie, the response and progression events both occurred while receiving study drug during the same treatment period).

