- c Patients who achieve and maintain disease control (ie, CR, PR, no evidence of disease, or SD) through to the end of the 12-month treatment period may restart and continue study drug upon evidence of PD (according to RECIST 1.1), with or without confirmation, during follow-up. Before restarting study drug, the Investigator should ensure patients still meet all of the inclusion criteria and none of the exclusion criteria for this study including re-consenting to treatment. To restart study drug the patient must not have received an intervening systemic anti-cancer therapy post study drug discontinuation. Patients should have a baseline tumour assessment within 28 days of restarting study drug, all further scans should occur every 8 weeks (relative to the date of restarting study drug). Patients who continue to receive re-treatment after the final DCO should receive tumour assessment scans and other assessments as per local clinical practice. It is recommended that the patients continue the scheduled site visits and Investigators monitor the patient's safety laboratory assessments prior to and periodically during the treatment with MEDI4736 in order to manage AEs in accordance with the MEDI4736 TMGs (refer to Section 5.5.3).

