- g Patients who achieve and maintain disease control (ie, CR, PR, NED, or SD) through to the end of the 12-month treatment period may restart study drug upon evidence of PD (according to RECIST 1.1), with or without confirmation, during follow-up. Before restarting study drug, the Investigator should ensure patients still meet all of the inclusion criteria and none of the exclusion criteria for this study including re-consenting to study drug. To restart study drug the patient must not have received an intervening systemic anti-cancer therapy post study drug discontinuation. Patients should have a baseline tumour assessment within 28 days of restarting study drug, all further scans should occur every 8 weeks (relative to the date of restarting study drug), or, if they receive re-treatment after the final DCO, patients should receive tumour assessment scans and other assessments as per local clinical practice. It is recommended that the patients continue the scheduled site visits and Investigators monitor the patient's safety laboratory assessments prior to and periodically during the treatment with durvalumab in order to manage AEs in accordance with the durvalumab TMGs (refer to Section 5.5.3).
- h Patients with confirmed PD who continue to receive study drug at the discretion of the Investigator (following consultation with the sponsor) can receive study drug for as long as the Investigator judges that they are gaining clinical benefit. Patients will have scans every 8 weeks (relative to the date of randomisation) while on study drug, or, if they receive re-treatment after the final DCO, patients should receive tumour assessment scans and other assessments as per local clinical practice. It is recommended that the patients continue the scheduled site visits and Investigators monitor the patient's safety laboratory assessments prior to and periodically during the treatment with durvalumab in order to manage AEs in accordance with the durvalumab TMGs (refer to Section 5.5.3). Patients with rapid tumour progression or with symptomatic progression that requires urgent medical intervention (eg, central nervous system metastasis, respiratory failure due to tumour compression, spinal cord compression) will not be eligible to continue to receive study drug. Study drug should be discontinued if there is confirmed progression of disease (PD) following a previous response (PR or CR) to study drug.

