## **8.4 Informed consent**

The Principal Investigator(s) at each centre will:

- Ensure each patient is given full and adequate oral and written information about the nature, purpose, possible risk and benefit of the study
- Ensure each patient is notified that they are free to discontinue from the study at any time
- Ensure that each patient is given the opportunity to ask questions and allowed time to consider the information provided
- Ensure each patient provides signed and dated informed consent before conducting any procedure specifically for the study
- Ensure the original, signed Informed Consent Form(s) is/are stored in the Investigator's Study File
- Ensure a copy of the signed Informed Consent Form is given to the patient

- Ensure that any incentives for patients who participate in the study as well as any provisions for patients harmed as a consequence of study participation are described in the informed consent form that is approved by an Ethics Committee.

The PGx component of the study (relating to DNA) is optional and will be detailed on a separate informed consent form.

For all patients who are treated through progression and patients who achieve disease control and restart study drug upon evidence of confirmed PD (according to RECIST 1.1) during follow-up, the Investigator should ensure patients do not have any significant, unacceptable or irreversible toxicities that indicate continuing treatment will not further benefit the patient. The patient must meet the inclusion and exclusion criteria specified in Section 4.3. The informed consent documents will specify that treatment beyond initial evidence of PD or re-treatment for progression during follow up is not the standard of care and that alternative treatment options, either locally licensed treatments or other clinical trials, are available for this patient population. Patients with rapid tumour progression or with symptomatic progression that requires urgent medical intervention (eg, central nervous system metastasis, respiratory failure due to tumour compression, spinal cord compression) will not be eligible to continue to receive study drug.

Patients who are eligible for re-treatment following final DCO for the study must sign the re-treatment informed consent prior to receiving durvalumab. Copies of the informed consent must be maintained with the patient's medical records.

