- The patient must provide signed, written and dated consent through the re-treatment informed consent form (criterion 1). This consent document will specify re-treatment upon progression during follow up is not the standard of care and that alternative treatment options, either locally licensed treatments or other clinical trials, are available for this patient population.
- A biopsy is mandated at the time of progression if more than 3 years have passed since randomisation as confirmation of true recurrence of the original tumour and not a new primary lesion; the Investigator must consult with the Study Physician if such sampling is not feasible.
- The patient must meet serum creatinine CL >40 mL/min by the Cockcroft-Gault formula (or by 24-hour urine collection as defined by the formula in protocol inclusion criterion 10) and the criterion for AST/ALT.

The patient should not enter re-treatment if any of the following exclusion criteria are fulfilled:

- Concurrent enrolment in another clinical study, unless it is an observational (non-interventional) clinical study or the follow-up period of an interventional study (criterion 4)
- Current or prior use of immunosuppressive medication within 28 days before the first dose of study drug, with the exceptions of intranasal and inhaled corticosteroids or systemic corticosteroids at physiological doses, which are not to exceed 10 mg/day of prednisone, or an equivalent corticosteroid (criterion 9)
- Any unresolved toxicity CTCAE >Grade 2 from previous anti-cancer therapy. Patients with irreversible toxicity that is not reasonably expected to be exacerbated by the investigational product may be included (eg, hearing loss) after consultation with the AstraZeneca/MedImmune study physician (criterion 11)
- Any prior Grade  $\geq 3$  irAE while previously receiving study treatment, or any unresolved irAE >Grade 1 (criterion 13)
- Be currently receiving, or have received in the interim period after stopping study drug, any chemotherapy, immunotherapy, biologic or hormonal therapy for cancer treatment. Note: Local treatment of isolated lesions, excluding target lesions, for palliative intent is acceptable (eg, by local surgery or radiotherapy) (drawn from criterion 14)

- Recent major surgery within 4 weeks prior to dosing (excluding the placement of vascular access) that would prevent administration of investigational product (criterion 15)

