Disease progression requires confirmation, the confirmatory scan should occur preferably at the next scheduled visit and no earlier than 4 weeks after the initial assessment of PD in the absence of clinically significant deterioration. Study treatment will continue between the initial assessment of progression and confirmation for progression. For all patients who are treated through progression and patients who achieve disease control (i.e., CR, PR or SD) through to the end of the 12 month treatment period and restart study treatment upon evidence of PD (according to RECIST 1.1), with or without confirmation, during follow-up, the investigator should ensure patients do not have any significant, unacceptable or irreversible toxicities that indicate continuing treatment will not further benefit the patient, and that the patient still meets all of the inclusion criteria and none of the exclusion criteria for this study including re-consenting to continue or restart treatment. To restart study treatment the patient must not have received an intervening systemic anti-cancer therapy post study drug discontinuation. Study drug should be discontinued if there is confirmed PD following a previous response (PR or CR) to study drug.

Patients with rapid tumour progression or with symptomatic progression that requires urgent medical intervention (eg, central nervous system metastasis, respiratory failure due to tumour compression, spinal cord compression) will not be eligible to continue to receive study drug.

Progression would be considered confirmed if the following criteria are met:

- $\geq 20\%$ increase in the sum diameters of target lesions (TLs) compared with the nadir at 2 consecutive visits with an absolute increase of at least 5 mm

The assessment of progression of $\geq 20\%$ increase in the sum diameters of TLs compared with the nadir is at the first progression time point relative to the nadir (the smallest sum of diameters and this may be at baseline or subsequent follow-up visit). The confirmed scan confirms the persistence of the $\geq 20\%$ increase relative to the nadir.

- and/or significant progression (worsening) of non target lesions (NTLs) or new lesions at the confirmatory PD time point compared with the first time point where progression of NTLs or new lesions identified
- and/or additional new unequivocal lesions at the confirmatory PD time point compared with the first time point new lesions identified.

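### Re-treatment eligibility is stated inconsistently: Protocol Sections 4.3 and 9.5.1 give different lists for the same long-term phase, and two footnotes and Section 8.4 differ again

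*Protocol*

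**What the plan says.** Four places in the current protocol bear on who may restart durvalumab.

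- **Section 4.3** sets out a subset of the entry criteria: renewed consent, creatinine clearance, AST/ALT, and a list of exclusions that includes "History of hypersensitivity to MEDI4736 or any excipient (criterion 20". Its closing paragraphs say that durvalumab-arm patients who progress after the data cut-off for the primary PFS and OS analyses must meet the same list when they are re-treated.
- **Section 9.5.1**, on data collection after those analyses, does not refer back to Section 4.3. It prints its own list under the words "The patient should not enter re-treatment if any of the following exclusion criteria are fulfilled". It also requires a biopsy if more than 3 years have passed since randomisation, a condition repeated in Table 11 footnote d.
- **Figure 2 footnote c** says that before restart "the Investigator should ensure patients still meet all of the inclusion criteria and none of the exclusion criteria for this study". Table 1 footnote g says the same. SAP Section 3.1 has a parallel sentence ("the patient still meets all of the inclusion criteria and none of the exclusion criteria for this study"), and so does footnote c of the flow chart in SAP Section 1.2.
- **Section 8.4** describes patients who "restart study drug upon evidence of confirmed PD (according to RECIST 1.1) during follow-up". The synopsis (duration of treatment), Figure 2 footnote c, Table 1 footnote g and Sections 4.3, 5.5.2 and 6.3 all allow restart whether or not the progression has been confirmed.

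**The concern.** A decision to give the drug again should rest on one list. Here a site gets a different answer depending on where it looks, and the difference covers a history of hypersensitivity to the study drug. Section 1.4.2 names hypersensitivity reactions among the important potential risks, and Section 5.5.3.1 counts them as adverse events of special interest.

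Criteria 18 and 19 describe conditions screened for at entry and unlikely to be new. Hypersensitivity can arise from the study treatment itself, so a patient who was clear of criterion 20 at entry may not be clear of it at re-treatment.

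The phase affected is the one in operation. The synopsis records that the endpoints had been met and the planned analyses concluded when Amendment 07 was finalised.

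**Working it through.** No power, alpha or event figure is involved. The check compares the criterion numbers printed in each list with the full lists in Sections 4.1 (10 inclusion criteria) and 4.2 (27 exclusion criteria).

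| | Section 4.3 | Section 9.5.1 | Figure 2 fn c, Table 1 fn g (literal) |
|---|---|---|---|
| Exclusions carried | 4, 9, 11, 13–24, 26, 27 | 4, 9, 11, 13–17, 21–24, 26, 27 | 1–27 |
| Count | 3 + 12 + 2 = 17 | 3 + 5 + 4 + 2 = 14 | 27 |
| Criteria 18, 19, 20 | present | absent | present |
| Biopsy beyond 3 years | absent | present | absent |

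**Section 4.3 against Section 9.5.1.** 17 − 14 = 3, and the three are criteria 18 (primary immunodeficiency), 19 (allogeneic organ transplant) and 20 (hypersensitivity). Nothing in the Section 9.5.1 exclusion list is missing from Section 4.3; the biopsy is the only item that runs the other way. The two lists are not for separate periods, because Section 4.3 extends itself to the period that Section 9.5.1 covers. Table 11 requires eligibility to be verified at progression but does not say against which of the two lists.

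**The footnotes.** Read literally, they add 27 − 17 = 10 exclusions to the Section 4.3 list: 1, 2, 3, 5, 6, 7, 8, 10, 12 and 25. Two of these settle the matter. Exclusion 2 covers earlier drug assignment in this study, which is true of every randomised patient. Exclusion 10 is "Prior exposure to any anti-PD-1 or anti-PD-L1 antibody", which is true of every patient who has had durvalumab. The number eligible on that reading is zero. Inclusion 5 (no progression after chemoradiation), read the same way, also collides with the trigger for re-treatment, which is progression.

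**What the rest of the protocol points to.** Sections 5.5.2, 6.3 and 8.4 send the reader to Section 4.3 for patients who restart. Figure 2 footnotes b and d and Table 1 footnote f cite Section 4.3 for the criteria relevant to treatment through progression and re-treatment. Table 2 footnote c cites it for re-treatment eligibility.

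**What catches hypersensitivity if only Section 9.5.1 is read.**

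- Sections 5.5.2.1 and 5.8 provide for discontinuation after an infusion reaction of Grade 3 or higher.
- Section 9.5.1 keeps criterion 13 (an earlier immune-related event of Grade 3 or higher, or an unresolved one above Grade 1).
- It also keeps criterion 27 (investigator judgement).

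Section 5.5.2.1 allows dosing to continue after an infusion reaction of Grade 2 or lower. Such a patient can complete 12 months and become a candidate, and the Section 9.5.1 list does not name the history.

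**The case against.** The strongest reply is that the protocol, read as a whole, has one list. Section 4.3 covers the long-term phase in terms, and most cross-references lead to it. Sections 4.3 and 9.5.1 are also not logically incompatible: a patient can satisfy both. Figure 2 footnote c goes on to fix the restart baseline scan and the later scan schedule, so it presupposes that some patients are eligible. The single word in Section 8.4 sits in a paragraph that itself refers to Section 4.3.

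Much of this stands, and it rules out three stronger readings that a reader might infer.

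- **That the protocol bars every patient from re-treatment.** This follows only from a literal reading of two footnotes that the operative sections contradict.
- **That Section 9.5.1 alone governs the long-term phase, so that a hypersensitive patient may be re-treated.** Section 4.3 applies its own list, including criterion 20, to that phase.
- **That the SAP misdirects sites.** The SAP is dated 22 March 2017 and the protocol 04 September 2019. The SAP is an analysis document that sites do not use to decide eligibility.

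Probable intent does not remove the conflict. Section 9.5.1 announces its list as the eligibility criteria and prints it in full, so a site has no prompt to look elsewhere. The two footnotes carry no qualification, although neighbouring footnotes do cite Section 4.3. The retained safeguards leave the lower-grade case to judgement, where Section 4.3 has an explicit exclusion.

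**Conclusion.** The inconsistency is real and can be confirmed by reading the protocol alone. Three exclusions and one biopsy requirement differ between two lists for the same phase. Two footnotes state a test that no patient already given the drug can pass if it is taken at its word. One section differs from six other places on whether progression must be confirmed.

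The consequence is limited. The residual safety gap is mainly a patient with lower-grade hypersensitivity assessed under Section 9.5.1 alone. The documents do not show how many patients that could be, nor whether any site has read the text that way. That the subset list was intended in place of the full criteria is an inference from the cross-references; the protocol does not say so.

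No confirmatory analysis depends on the point. SAP Section 4.1 treats re-treatment efficacy (site investigator data only) and safety as optional separate summaries. It matters because it concerns who may receive the drug again, and it should be corrected.

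**What to change.** The sponsor should reconcile Section 4.3, Section 9.5.1 with Table 11, Figure 2 footnote c, Table 1 footnote g and Section 8.4. The result should be one re-treatment eligibility list, stated once and cited everywhere else. Three items need an explicit decision, so that none is lost or added by accident:

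1. whether criteria 18, 19 and 20 apply in the long-term phase;
2. whether the biopsy beyond 3 years, now found only in Section 9.5.1 and Table 11, belongs in the single list. Replacing Section 9.5.1 by a bare reference to Section 4.3 as it stands would drop it from that section's eligibility list;
3. whether progression must be confirmed before restart.

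Which criteria apply is the sponsor's clinical decision, and none is proposed here. The parallel wording in SAP Section 1.2 (flow chart footnote c) and Section 3.1 can be aligned at the next SAP revision.

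The cost is a clarifying protocol amendment, handled under Section 8.5. Reconciling the text does not in itself add procedures or data collection.
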